### 2.3.2 Pilot testing

Based on feedback from this initial trial of the DSM-H, [name] refined the clinical education programs to reduce pharmacology content and increase content on recognition of dementia and non-pharmacologic management and working with caregivers. Drs. [name] and [name] performed a site controlled trial of the DSM-H at 2 divisions of a large HHC agency and retrospectively collected OASIS and chart data for PWD on admission and at the first 60-day re-certification or discharge from HHC. Overall, during the study period 158 PWD were seen by the control site and 174 by the intervention site. Overall, patients were older, primarily spoke English or Spanish, were either Medicare or dual Medicare/Medicaid insured, and were admitted either from home or the acute care setting (See Appendix A). There were fewer black/African American participants in the control, the only clinically significant difference (34.2% vs 51.7%;  $p=.0002$ ). Overall, we found in multivariate analysis that recognition of pain, depression, and behavioral symptoms, were all clinically and statistically significantly higher in the intervention group, and there were significantly increased odds of analgesics use (OR=2.01;  $p<.05$ ) and decreased odds of antipsychotic use (OR=0.53;  $p<.05$ ) in the intervention cohort. ***These results show the DSM-H has the potential to be improve patient care and the QOL of PWD receiving HHC.***

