***Aim 3: Assess the effects of the DSM-H on healthcare utilization in the PWD.***

H3: PWD cared for by a HHC team utilizing the DSM-H performance improvement program will show a reduction in emergency room visits and hospital admissions compared to the control (usual care) group, and a greater number of outpatient visits.

The primary outcomes to be measured are the number of emergency room visits and hospital admission rates of the PWD at 30 and 60 days. It will be measured through interviews with the informal caregiver using the Resource Utilization Inventory.

CONFIDENTIAL

This material is the property of the NYU School of Medicine and Langone Medical Center. Do not disclose or use except as authorized in writing by the study sponsor  
 Interventional Template Version: 28 APR 2017

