#### Enrollment/Baseline Visit

**Visit 1, (Day 0/1)** the following surveys will be collected during visit one. Surveys administered to the PWD are indicated by their QDRS score:

- PAINAD (if QDRS>12)
- FAM-CAM
- Brief Pain Inventory Short Form (BPI; if QDRS $\leq 12$ ).
- Quality of Life in Alzheimer’s Disease (QOL-AD) (if QDRS  $\leq 12$ )
- Neuropsychiatric Inventory Questionnaire (NPI-Q)
- Caregiver Targeted Quality of Life Tool (CGQOL):
- Public Health Questionnaire 9 (PHQ-9)
- Zarit Burden Inventory
- SF-12
- Charlson Comorbidity

CONFIDENTIAL

This material is the property of the NYU School of Medicine and Langone Medical Center. Do not disclose or use except as authorized in writing by the study sponsor

- Katz ADLs and Lawton iADLS (through the QOL-AD)
- The Short Assessment of Health Literacy (SAHL)
- Other non-instrumented questions that will be asked include sociodemographics (DOB, sex, highest education level attained, race, ethnicity, primary language, religion, marital status, household members, number type and frequency of unpaid and paid caregivers, medication record and use, primary care provider name and contact for both PWD and caregiver).
- Information obtained from the chart includes: Number of visits by the home healthcare staff by type, comorbidities, COVID-19 questions.

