##### **Visit 3 (Day 30+/-3)**

The following surveys will be administered for visit three:

*Surveys administered to the PWD are indicated by their QDRS score:*

- PAINAD (If QDRS >12)
- FAM-CAM
- BPI (If QDRS≤12)
- NPI-Q
- Katz ADLs and Lawton iADLS (through the QOL-AD)
- Resource Utilization Inventory
- Non-instrumented: Medication Record and Usage, Resource Utilization Inventory, AE and SAE, COVID-19 questions

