### 7.2.5 Final Study Visit

#### **Final Study Visit (Visit 4, Day 60+5)**

The following surveys will be administered for visit four:

*Surveys administered to the PWD are indicated by their QDRS score:*

- PAINAD (If QDRS >12)
- FAM-CAM
- BPI (If QDRS≤12)
- QOL-AD (If QDRS≤12)
- NPI-Q
- CGQOL:
- Public Health Questionnaire 9 (PHQ-9)
- Zarit Burden Inventory
- SF-12
- Charlson Comorbidity
- Resource Utilization Inventory

CONFIDENTIAL

This material is the property of the NYU School of Medicine and Langone Medical Center. Do not disclose or use except as authorized in writing by the study sponsor

- HHCAHPS
- Katz ADLs and Lawton IADLS (through the QOL-AD)
- Non-instrumented: Medication Record and Usage, Resource Utilization Inventory, AE and SAE
- Information obtained from the chart includes: Number of visits by the home healthcare staff by type, comorbidities, COVID-19 questions.

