## 10.4 Description of Statistical Methods

### 10.4.1 General Approach

Data Analysis will be performed using SAS 9.4. We will perform statistical tests to examine baseline differences between the quality improvement program and control groups. We will then perform unadjusted comparison of both primary outcomes (patient and caregiver quality of life, emergency room visits) and secondary outcomes (pain, BPSD, delirium, caregiver depression burden, and burnout, hospital and emergency room admissions) between groups. We will focus on the endpoint measure for quality of life, and 30 and 60-day outcomes for emergency room utilization. For primary and secondary outcomes, we will perform a time trend analysis using a mixed effects linear model (PROC MCM). Mixed effects regression is used to analyze longitudinal data with repeated measures accounting for intra-individual and group clustering. We intend to use multivariate mixed effects regression modeling as opposed to traditional linear modeling or ANOVA in order to control for unobservable confounding variables that are constant over time but differ across PWD and/or caregivers. For both primary and secondary outcomes, we will then repeat the above analyses adjusting for baseline variables as covariates for a more efficient measurement of the effects of the quality improvement program. We will also perform correlation analyses to explore the relationship between pain and BPSD, and PWD and caregiver QOL through plotting scores over time and then if a significant correlation is present through adding to our mixed effect model. For utilization data, we will perform logistic regression to examine whether the patient is more or less likely to have a hospitalization or ER visit compared when receiving the quality improvement program at 30 and 60 days. We will then perform a Poisson Count Regression to compare the total number of hospitalizations and ER visits at each timepoint. In these models we will utilize a random effect to measure for clustering.

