**Table 2. Variables and Timing of Data Collection from PWD-Caregiver Dyads**

Variable	Instruments or Measures	Items	Min.	Timing of Data Collection (Days)							
				Patient				Caregiver			
				0	15	30	60	0	15	30	60
Consent				✓				✓			
Patient-Centered Outcomes											
Stage of Dementia	Quick Dementia Rating Scale 	10	5					✓			
BPSD	Neuropsychiatric Inventory Questionnaire	13	5					✓	✓	✓	✓
Quality of life	Quality of Life in Alzheimer's Disease 	13	5					✓			✓
Pain	Brief Pain Inventory Short Form	9	5	✓	✓	✓	✓				
Pain	PAINAD	5	3	✓	✓	✓	✓				
Patient Satisfaction	HHCAHPS	32	7						✓	✓	✓
Pain	Analgesic use (collected by RA on each dyad visit)	1	1					✓	✓	✓	✓
BPSD	Antipsychotic use (collected by RA on each dyad visit)	1	1					✓	✓	✓	✓
Delirium	FAM-CAM 	11	3					✓	✓	✓	✓
Caregiver Centered Outcomes											
Quality of Life	Caregiver Targeted Quality of Life 	80	20					✓			✓
Depression	Public Health Questionnaire 9 	9	3					✓			✓
Burden	Zarit Burden Inventory 	22	10					✓			✓
Health	SF-12 	12	3					✓			✓
Utilization Outcomes											
Healthcare Utilization	Resource Utilization Inventory 	13	5					✓		✓	✓
Sociodemographics											
Sociodemographics	Date of birth, sex, education, race, ethnicity	6	4	✓				✓			
Language, Religion and Culture	Primary language, religion, literacy (SAHL-SE) 	3	3	✓				✓			
Supports											
Social Support	Marital status, household members	2	<1	✓					✓		
Other unpaid caregivers	# individuals, # visits, #hrs/week	3	1	✓	✓	✓	✓	✓			
Paid Caregiver	# visits, hrs/week	2	1	✓	✓	✓	✓	✓			
Home nurse visits	# visits (chart)	1				✓	✓				
Physical/occupational therapy	# visits (chart)	2				✓	✓				
COVID-19 Effects on Caregiving	University of Pittsburgh COVID Caregiving Questionnaire and Investigator Derived from the Resource Utilization Inventory	18	6						✓		
Health and Functional Status											
Functional Status	Katz Activities of Daily Living  , Lawton Instrumental Activities of Daily Living 	12	2	✓	✓	✓	✓				
Comorbidities	Charlson comorbidity Questionnaire  (chart for patient, interview for caregiver)	17	3	✓					✓		

CONFIDENTIAL

This material is the property of the NYU School of Medicine and Langone Medical Center. Do not disclose or use except as authorized in writing by the study sponsor

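### Table 2 schedules the Resource Utilization Inventory at day 0, but the visit 1 list omits it and sections 3.1 and 3.2 time Aim 3 at 30 and 60 days only

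*Combined protocol and SAP*

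**What the plan says.** **Visit 1 (section 7.2.2).** The protocol states that "the following surveys will be collected during visit one" and lists PAINAD, FAM-CAM, BPI, QOL-AD, NPI-Q, CGQOL, PHQ-9, Zarit, SF-12, Charlson, ADLs and IADLs, SAHL, sociodemographic and medication questions, and chart items. No utilisation instrument appears.

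**Visits 3 and 4.** Both lists include it: "Non-instrumented: Medication Record and Usage, Resource Utilization Inventory, AE and SAE, COVID-19 questions" at day 30, and "Non-instrumented: Medication Record and Usage, Resource Utilization Inventory, AE and SAE" at day 60.

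**Table 2.** The row for the "Resource Utilization Inventory" (13 items, 5 minutes) is ticked for the caregiver at days 0, 30 and 60. Caregiver day 15 and all four patient columns are blank.

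**Objectives.** Section 3.1 sets the Aim 3 primary outcomes as "emergency room visits and hospital admission rates of the PWD at 30 and 60 days". Section 3.2 gives the same two times for outpatient visits and primary care contacts.

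**Analysis (10.4.1).** For primary and secondary outcomes, the analyses are to be repeated "adjusting for baseline variables as covariates for a more efficient measurement of the effects of the quality improvement program". The covariates are not named. The logistic and Poisson models for utilisation are described after that sentence, with a random effect for clustering and nothing else.

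**The concern.** The protocol gives two answers to whether utilisation before enrolment is measured. Staff working from section 7.2.2 would not ask about it; staff working from Table 2 would. A baseline missed at enrolment can be recovered later only by more distant recall.

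Prior ER and hospital use is the baseline variable closest to the Aim 3 outcomes. The pilot report in 2.3.2 says that patients "were admitted either from home or the acute care setting", so recent hospital use probably differs between patients here too. Only 20 teams are randomised, which leaves room for chance imbalance. Section 10.4.4 compares arms on demographics, health literacy, function and comorbidity, but not on prior use. Without a day-0 measure, the adjusted analysis cannot use this variable, and its balance across teams cannot be examined directly. Section 10.5 gives no power calculation for Aim 3, so nothing shows that precision is there to spare.

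**Working it through.** **1. Is the day-0 tick real?** The Table 2 row has 12 fields. The last eight are the patient columns (0, 15, 30, 60) and then the caregiver columns (0, 15, 30, 60). They read blank, blank, blank, blank, tick, blank, tick, tick. In a block of four caregiver columns, tick-blank-tick-tick can only mean days 0, 30 and 60. A column shift in PDF extraction is therefore unlikely for this row.

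**2. The passages side by side.**

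| Place | Day 0 | Day 30 | Day 60 |
|---|---|---|---|
| Table 2 | yes | yes | yes |
| Visit lists, section 7.2 | no | yes | yes |
| Sections 3.1 and 3.2 (Aim 3 timing) | not mentioned | yes | yes |

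Table 2 is the only place with a day-0 administration.

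**3. What would baseline use be worth?** The plan has no figure to reproduce, so this is an illustration.

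From the documents:
- Section 4.2.1 equates a 10% reduction with 220 fewer ER visits and 63.8 fewer admissions per 1000 patients. This implies λ = 220/(.10 × 1000) = 2.2 ER visits and λ = 63.8/(.10 × 1000) = .638 admissions per person.
- Section 10.5 has 10 teams per arm and 15 completed dyads per team. It uses an ICC of .05, justified for the power analyses generally and not for utilisation.

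Assumed:
- patient-level dispersion 1;
- ICC .05 applied to utilisation;
- prior use explains R² = .10 to .20 of the between-patient dispersion.

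Formula: Var(log RR) = (2/10) × [(1/λ + 1 − R²)/15 + CV²], with between-team CV² = (.05/.95)/λ. R² reduces only the dispersion term of 1. The 1/λ term is Poisson sampling noise, which no covariate removes.

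- **Admissions.** 1/λ = 1.567 and CV² = .0825. With R² = 0, SE = √(.2 × [2.567/15 + .0825]) = .225. With R² = .10, SE = √(.2 × [2.467/15 + .0825]) = .222, a cut of 1.3%. With R² = .20, SE = √(.2 × [2.367/15 + .0825]) = .219, a cut of 2.7%.
- **ER visits.** 1/λ = .4545 and CV² = .0239. With R² = 0, SE = √(.2 × [1.4545/15 + .0239]) = .155. With R² = .10, SE = √(.2 × [1.3545/15 + .0239]) = .151, a cut of 2.8%. With R² = .20, SE = √(.2 × [1.2545/15 + .0239]) = .147, a cut of 5.7%.

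**4. Sensitivity to the ICC definition.** If the ICC refers to total patient variance, CV² = (.05/.95)(1/λ + 1), which is .135 for admissions and .077 for ER visits. The unadjusted SEs become .247 and .186, and the cuts become 1.1-2.2% and 1.9-3.9%. At a given R², the gain is smaller when events are rarer, so an ER rate below 2.2 would move that figure towards the one for admissions.

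**The case against.** **Two readings against one.** Sections 3.1 and 3.2 agree with the visit 1 list, so the Table 2 tick stands alone. Table 2 also departs from the visit lists elsewhere: HHCAHPS is ticked at days 15, 30 and 60, but among the visit lists only visit 4 has it. This stands in part. The documents do not settle which version was intended. However, sections 3.1 and 3.2 give outcome times, which do not exclude a baseline measure.

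**No prespecified model is lost.** This stands. A reader might infer that a planned Aim 3 analysis becomes impossible. The documents do not support that. Section 10.4.1 names no covariates, and its adjustment sentence comes before the utilisation models, so it may not have been meant to cover them. Aim 3 counts events after enrolment, and the arms can be compared without a baseline.

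**Readmissions.** Section 4.2.1 speaks of readmissions, so a reader might infer that the outcome itself cannot be built without hospital history. But section 3.1 and hypothesis H3 in 10.2 define it by hospital admissions and ER visits.

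**Other sources may serve.** This stands in part. OASIS data and the agency health record are collected (6.1.6, 7.2.6) and might allow a partial balance check. Neither section says that they hold counts of prior ER visits or admissions.

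**The assumptions are soft.** This stands. The documents give no dispersion, R² or ICC for utilisation. Applying R² to the whole patient-level variance would give cuts of 3-8%, but that credits the covariate with removing Poisson noise and should not be used.

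**Central forms may already settle it.** Surveys are entered in Qualtrics with forced entry, and the instrument set and study manual are separate attachments. What was built may be uniform, but the protocol does not show which version it follows.

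**Conclusion.** The inconsistency is real and should be resolved. If the visit 1 list is followed, the trial has no caregiver-reported utilisation from before enrolment. The adjusted analyses in 10.4.1 cannot use it, and balance across the 20 teams on prior use cannot be checked directly.

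The consequence is limited. One visit list serves both arms, so the omission creates no bias and the unadjusted comparison stands. Under the assumptions shown, the lost precision is roughly 1-3% of the standard error for admissions and up to about 6% for ER visits. Nor would adjustment make Aim 3 well powered: the 10% reduction in 4.2.1 is log(.9) = −.105, which is smaller than one standard error even after adjustment (.219 for admissions and .147 for ER visits at R² = .20). The case for acting is that an instrument already in Table 2 gives a direct balance check and a small gain at little cost.

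**What to change.** - **Schedule.** Reconcile section 7.2.2 and the timing statements in 3.1 and 3.2 with Table 2 by listing the Resource Utilization Inventory for the caregiver at visit 1. State a fixed look-back period that ends at home health admission, so that the baseline precedes any care by the assigned team. If no day-0 administration is intended, remove the Table 2 tick and say whether OASIS or chart data will supply prior use.
- **Analysis.** In 10.4.1, name baseline ER visits and admissions as covariates in the adjusted logistic and Poisson models, and say that the adjustment covers those models. Add a missing-baseline indicator for dyads already enrolled without the instrument.
- **Balance.** Add prior utilisation to the baseline comparison in 10.4.4.

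**Cost.** About 5 minutes per caregiver at visit 1 (Table 2's own figure) where it is not already done, one sentence in 10.4.1, and the matching edits to the visit list, 3.1, 3.2 and 10.4.4.

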### 7.2.3 Intermediate Visits:

#### 7.2.4

##### **Visit 2 (Day 15+/-3)**

The following surveys will be administered for visit two:

*Surveys administered to the PWD are indicated by their QDRS score:*

- BPI (If QDRS<12)
- PAINAD (If QDRS >12)
- FAM-CAM
- NPI-Q
- Katz ADLs and Lawton iADLS (through the QOL-AD)
- Non-instrumented: Medication Record and Usage, AE and SAE

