### **3.2 Secondary Objectives**

The secondary objectives of Aim 1 are to assess the effects of the performance improvement program on pain and individual BPSDs in the PWD, and the use of antipsychotic and analgesic. They will be measured at all four time points (0, 15, 30, and 60 days). BPSD will be measured using the NPI-Q. The type of pain assessment administered to the PWD will depend on their level of cognitive impairment. The level of impairment will be determined by the Quick Dementia Rating System (QDRS) score. The PWD who obtains a score of  $\leq 12$  will receive the Brief Pain Inventory Short Form^103 and those whose score  $\geq 12$  on the QDRS will receive the PAINAD which will be used to measure pain at rest and with movement. All PWD subjects will be assessed for pain during each visit using the respective measure.

The secondary objectives of Aim 2 are to assess the effects of the performance improvement program on informal caregiver burden, depression, and functional health and well-being. The PHQ-9 will be used to measure caregiver depression, the Zarit Burden Interview for caregiver burden and the SF-12 for caregiver health at 0 and 60 days.

The secondary objectives of Aim 3 are to assess the effects of the performance improvement program on the number of outpatient visits and contacts with the primary care provider. These will be measured through interviews at 30 and 60 days with the Resource Utilization Inventory.

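### At a QDRS of exactly 12 the pain-tool rules conflict: both tools under section 3.2, the BPI alone at visits 1, 3 and 4, and no tool at visit 2

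*Combined protocol and SAP*

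**What the plan says.** Section 3.2 names pain among the secondary outcomes of Aim 1 and sets the schedule: "They will be measured at all four time points (0, 15, 30, and 60 days". It then chooses the tool by QDRS score. On one side, "The PWD who obtains a score of $\leq 12$ will receive the Brief Pain Inventory Short Form"; on the other, "those whose score $\geq 12$ on the QDRS will receive the PAINAD". It closes with a general rule: "All PWD subjects will be assessed for pain during each visit using the respective measure".

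The visit lists in section 7.2 repeat the choice with different symbols:

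- Visit 1 (section 7.2.2): "PAINAD (if QDRS>12", and the BPI at 12 or below.
- Visit 2 (section 7.2.4): "BPI (If QDRS<12" and "PAINAD (If QDRS >12".
- Visit 3 (section 7.2.4): "BPI (If QDRS≤12", and the PAINAD above 12.
- Visit 4 (section 7.2.5): the same split as visit 3.

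Table 2 ticks both tools for the patient at days 0, 15, 30 and 60 and attaches no QDRS condition to either. It schedules the QDRS itself at day 0 only.

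**The concern.** These are operative data-collection instructions. Staff work from them, and a survey programmer would build the branching from them. A PWD who scores exactly 12 falls under different instructions depending on which page is open, so two sites could each follow the protocol and collect different data.

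Two things are at stake, depending on which text is followed. Under the visit lists, a scheduled pain score is never requested at day 15. Section 11 relies on forced entry in Qualtrics to limit missing data, but forced entry acts only on questions that are displayed. If the branching was built from the visit 2 list, nothing would flag the gap. Under section 3.2, the same PWD would have a BPI and a PAINAD score at each visit, and section 10.4.1 does not say which of the two enters the pain analysis.

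**Working it through.** The plan gives no figure to reproduce here. The check sets the cut-offs side by side and applies each to every possible score.

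**Is a score of 12 possible in the trial?** Yes. Section 5.1 admits PWD with a QDRS of 6 or more.

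**Which tool does each rule assign?**

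| Source | BPI if | PAINAD if | Below 12 | Exactly 12 | Above 12 |
|---|---|---|---|---|---|
| Section 3.2 | ≤12 | ≥12 | BPI | BPI and PAINAD | PAINAD |
| Visit 1 | ≤12 | >12 | BPI | BPI | PAINAD |
| Visit 2 | <12 | >12 | BPI | none | PAINAD |
| Visit 3 | ≤12 | >12 | BPI | BPI | PAINAD |
| Visit 4 | ≤12 | >12 | BPI | BPI | PAINAD |
| Table 2 | no condition | no condition | both ticked | both ticked | both ticked |

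Evaluating the first five rows at scores of 6, 11, 11.5, 12, 12.5, 13 and 20 confirms this. All five agree on exactly one tool at every tested value except 12. Half-point values were included so that the result does not depend on the scoring step.

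**What follows for a PWD who scores 12?**

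- Visit lists followed: BPI at days 0, 30 and 60, and nothing at day 15. That is three of the four scheduled assessments, all on one scale. It contradicts the each-visit rule and the four-time-point schedule in section 3.2, and the day-15 ticks in Table 2.
- Section 3.2 followed: both tools at days 0, 15, 30 and 60. Nothing is missing, but there are two scores per visit on different scales.

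**How many PWD?** The documents give no distribution of QDRS scores, so no count can be derived. For scale only, each 1% of PWD scoring exactly 12 would be 0.01 × 345 = 3.45 of those enrolled, or 0.01 × 300 = 3 of those evaluable (section 5.6). If the share were 2% to 5%, which is an assumption without support in the documents, this would be 345 × 0.02 = 6.9 to 345 × 0.05 = 17.25 enrolled PWD, or 6 to 15 of the 300 evaluable.

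**The case against.** The strongest reply is that this is a typing slip. Three of the four visit lists use the same clean split, section 3.2 requires pain to be assessed in everyone at each visit, and Table 2 ticks both tools at day 15. Against that, one missing bar under a less-than sign at visit 2 is unlikely to be intended. A schedule table also shows when a tool is used and need not say for whom. This is plausible, and the actual branching, which is not in the documents, may be correct. But the overlap in section 3.2 is a separate conflict that does not depend on visit 2, and an instruction of this kind needs correcting even if the intent can be guessed.

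The second reply is that the analysis would hardly notice. H1 is stated at the end of the 60-day period, and visits 1 and 4 do not have the gap. The mixed model in section 10.4.1 can use the remaining three observations. Section 5.7.2 already accepts missed intermediate visits. Any gap would depend on a recorded score under the same rule in both arms. All of this stands, and it limits the point to a minor one.

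A reader might infer more: that these PWD both lose the day-15 score and carry two scales at the other visits, so that the repeated-measures pain analysis is damaged by systematic missingness and by mixed instruments. The documents do not support that. Section 3.2 covers every visit, so following it fills day 15; following the visit lists leaves the BPI alone at the other three visits. The combination arises only if staff switch rules between visits. Using the BPI for some PWD and the PAINAD for others is the design for the whole sample, and the day-0 QDRS score gives no reason for a change of tool within a person.

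**Conclusion.** The inconsistency is real and can be verified from the text: at a QDRS of exactly 12 the protocol assigns two pain tools, one, or none, depending on the section. The consequence is conditional. Either one intermediate score of a secondary outcome is missing, or each visit has two scores with no rule for which counts.

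The effect is confined to PWD at that single value, in unknown number. No primary endpoint or power figure is touched, and no mechanism for bias between arms is shown. Whether any data were actually lost depends on the survey branching, which the documents do not contain. This is a drafting inconsistency worth correcting because the correction is nearly free. It does not threaten the pain analysis.

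**What to change.** Reconcile section 3.2, the four visit lists and Table 2 to one partition, so that each QDRS value maps to exactly one pain tool at every visit. The split already written at visits 1, 3 and 4 does this. Adopting it would change one symbol in section 3.2 (the PAINAD condition) and one at visit 2 (the BPI condition). Add the QDRS condition to the two pain rows of Table 2, for example as a footnote.

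Then run a test record with a score of 12 through the survey at all four visits and confirm that exactly one tool appears each time. If dyads have already been enrolled under the current text, count the PWD who scored 12 and list which tools were recorded at each visit. That replaces the unknown number with a known one.

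The cost is two symbols, one table note and a short branching check, with no change to sample size, visit burden or the analysis model.
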